**8.5. Research Measures.**

See **Table 8.2** for the schedule of assessments.

**8.5.1. Diagnostic Assessment.** To make the diagnosis of cannabis dependence, the Structured Clinical Interview for DSM-IV (SCID) (First 1996) will be used.

**8.5.2. Drug and Alcohol Use Assessment.**

**8.5.2.a. Urine Screens.** The primary outcome measure will be cannabis use, as measured by twice-weekly quantitative urine screens during treatment. Cannabis is a particularly challenging drug of abuse for measuring outcome because of the *false-positive* urine screens that can occur as the result of long-term accumulation of cannabis metabolites. In an attempt to avoid false-positive results, we will obtain 2 supervised urine samples weekly: 1 at the medical visit and 1 on another day, ordinarily with 3-4 days separation from the clinical visits (e.g., Monday-Thursday, Tuesday-Friday, or Monday-Friday); this should maximize the time frame covered by our urine screens. We will send the urine samples to Quest Diagnostics Laboratory (Cambridge, MA, a NIDA-certified laboratory), where the urines will be screened by immunoassay for the THC metabolite 11-nor-carboxy- $\Delta$  9-tetrahydrocannabinol (THC-COOH) as well as other drugs of abuse. Urine creatinine concentrations will also be measured to assess urine concentration. The threshold for detection of THC-COOH will be 20 ng/ml. Samples positive for this metabolite will undergo further analysis by gas chromatography-mass spectroscopy to obtain quantitative THC-COOH concentration; we will then calculate the ratio of this metabolite to urine creatinine concentration. We will adopt the method of Heustis and Cone (1998) to differentiate new marijuana use from residual drug excretion as a result of previous use; these recommendations are based on their controlled clinical studies of urinary excretion profiles of creatinine and marijuana metabolites following marijuana administration in humans. We will label a urine negative (i.e., abstinent from cannabis) if 1) the ratio of THC-COOH to creatinine in the urine does not increase by >50% from the ratio obtained in the previous urine screen, and 2) the participant also reports using no cannabis since the previous urine test.

**McLean Hospital Application to the Institutional Review Board (IRB)  
Nabilone for Cannabis Dependence Detailed Protocol**

**8.5.2.b. Self-Report.** We will use 3 methods of self-report in an effort to determine the most appropriate and effective method for use in this population. An ActiWatch Score will be determined via compact, wrist-worn, battery-operated activity monitors that are excellent devices for monitoring multiple drug use, drug craving, and sleep/wake activity (Licata et al., under review). We will provide participants with a packet of 1 page, self-addressed, prepaid postage Daily Diary pages which participants will be asked to fill out between 7:00 and 9:00 a.m. each day and hand them in during their weekly visits to the lab. The diary consists of a series of questions about cannabis and other drug use as well as eating and sleeping habits. During the weekly visits, we plan to collect cannabis use data using the Timeline Follow Back(TLFB) (Sobel and Sobel 1992) protocol that was developed for alcohol.

**8.5.2.c. Other Drug and Alcohol Use Assessment.** Severity of cannabis and other substance use and its associated problems will be assessed at baseline and weeks 4, 10, and 14 with the Addiction Severity Index (ASI, 5th edition) (McLellan et al. 1992), a widely-used and independently-validated interview that measures the severity of problems in 7 areas of functioning that are frequently affected in patients with SUDs: drug use, alcohol use, employment, legal status, medical condition, social functioning, and psychological status. In addition to our primary focus on cannabis use (urine screens plus days of use), we will examine other substance use (using urine screens plus days of other substance use). We will use this method to determine the number of days of cannabis use and of any substance use (and conversely, days of abstinence). We will examine ASI composite scores as secondary measures of substance use outcome. We will also use the self-administered Drug and Alcohol Use Questionnaire. This measure, administered at baseline, addresses the context of lifetime and recent drug and alcohol use, as well as sociodemographic data. At each treatment visit, patients will complete a brief Weekly Drug and Alcohol Use Inventory, indicating their number of days using marijuana, other drugs, and alcohol during the previous week. The Marijuana Goals Questionnaire (Griffin et al. 1989) is a brief questionnaire administered at baseline to assess treatment goals, specifically, whether a participant is seeking abstinence or reduction in cannabis use. A 12-item self-administered questionnaire, the Marijuana Craving Questionnaire (MCQ), will be used to assess craving at baseline and weekly during treatment and at the 14-week follow-up visit (Heishman et al. 2009). A short form of the Marijuana Withdrawal Checklist (MWC) will be used to assess withdrawal symptoms at baseline and weekly during treatment and at the 14-week follow-up visit (Budney et al. 1999). If there is a discrepancy among results obtained by these methods of substance use assessment, we will meet with the participant and have a conversation about their substance use. After the conversation, we will use our clinical judgment to determine the level of use that we believe is most accurate for that participant. A new 6-page questionnaire that we created, the Marijuana Perceptions of Risk and Experiences Questionnaire (MPRE), will be distributed at baseline, and once during weeks 4, 10 and 14 to assess each participant's perceptions of cannabis risk/harm and his or her motivations to quit/continue using cannabis throughout the course of treatment.

**8.5.3. Mood and Impulsivity Assessments.** We will monitor participants' mood throughout the study using 3 assessments. The Beck Anxiety Inventory (BAI) is a 21-

**McLean Hospital Application to the Institutional Review Board (IRB)  
Nabilone for Cannabis Dependence Detailed Protocol**

item self-report measure that can be used to assess the severity of anxiety. The Quick Inventory of Depressive Symptomatology (QIDS-SR) is a short self-report questionnaire for depressive symptoms used successfully in the STAR\*D project. The Positive and Negative Affect Scale (PANAS) is a 20-item self-report scale in which mood variables are rated by participants on a 1-5 scale. The Barratt Impulsiveness Scale (BIS-11) is a commonly used tool to measure impulsivity in various neuropsychological disorders as well as in substance abuse. Three dimensions can be assessed using this scale, which include Cognitive Impulsivity, Motor Impulsivity, and Non-planning Impulsivity.

**Table 8.1** Schedule of Measures

Measure	Baseline	Weekly	Weeks 4 &10	Week 14
Diagnostic Assessment				
1. Structured Clinical Interview for DSM-IV a	X			
Drug and Alcohol Assessment				
2. Quantitative Urine Toxicological Analysis b	X	X b	X	X
3. Addiction Severity Index	X		X	X
4. Drug and Alcohol Use Questionnaire	X			
5. Weekly Drug and Alcohol Use Inventory	X	X	X	X
6. Marijuana Goals Questionnaire	X			
7. Marijuana Craving Questionnaire	X	X	X	X
8. Marijuana Withdrawal Checklist	X	X	X	X
9. Marijuana Perceptions of Risk and Experiences	X		X	X
Mood and Impulsivity Assessment				
10. Quick Inventory of Depressive Symptomatology	X		X	X
11. Beck Anxiety Inventory	X		X	X
12. Positive and Negative Affect Scale	X		X	X
13. Barratt Impulsiveness Scale	X		X	X
Medical & Safety Assessment (medical visits)				
14. Physical examination	X			X
15. ECG	X			X
16. Urine pregnancy test	X		X	X
17. Laboratory tests c	X			X
18. Adverse Events & Side Effects	X	X		X
19. Columbia Suicide Severity Rating Scale	X	X	X	X

aFull SCID at baseline

bTwice a week during treatment;

cTests include urinalysis, liver function tests, electrolytes, complete blood count, & blood chemistries

**8.6. Medication Adherence Assessment.** The proposed studies involve chronic administration of medication given under double-blind conditions. Three methods of

**McLean Hospital Application to the Institutional Review Board (IRB)  
Nabilone for Cannabis Dependence Detailed Protocol**

medication adherence will be used as multiple methods are preferred (Weiss 2004): 1) pill counts will be made; 2) participants will record when they take their capsules on the ActiWatch-Score device; 3) urinary riboflavin levels (a 25 mg dose will be given with each dose of medication) will be measured using a UV spectrophotometer. If there is a discrepancy among results obtained by these methods, we will meet with the participant and have a conversation about their medication adherence. After the conversation, we will use our clinical judgment to determine the level of adherence that we believe is most accurate for that participant.

**8.8. Data Management**

All data collected will be de-identified with participant ID numbers and used for research purposes only. Written records will be kept in a locked file cabinet in a locked office. They will be destroyed after 5 years. Computerized data files will also be de-identified with participant ID numbers and kept in a password protected file on a password protected computer.

**8.9. Statistical Analysis**

The primary data analysis will be an intent-to-treat analysis, which includes all randomized participants. Of note, every attempt will be made to continue assessing participants even if they drop out of treatment. In addition, we will replicate all analyses with the completers only. The primary and secondary outcome variables are intended to explore various aspects of response to therapy and to help define a clinically meaningful response. The primary outcome measures, Actiwatch-scores, daily diaries, TLFB self-report data, in addition to quantitative urinary THC metabolites, have been chosen for their ability to indicate daily use of cannabis by relying on self-report of use.

Specifically, for assessing the effect of nabilone on cannabis use patterns, we propose to use the generalized estimating equations (GEE) approach to longitudinal analysis, appropriately accounting for the positive correlation among repeated urine screen assessments within the same individual.

Analyses of secondary substance use outcomes will focus on the number of days of cannabis use and of any substance use (and conversely, days of abstinence) during treatment and post-treatment follow-up. In addition, we will also examine the ASI Drug and Alcohol composite scores. Frequency of days of cannabis use (and any substance use and days of abstinence) will be analyzed via a log-linear (or Poisson) regression model, controlling for pre-treatment frequency of days of cannabis use. Although log-linear regression methods are considered appropriate for the analysis of count or frequency data, in many biomedical applications, count data have variability that far exceeds that predicted by the Poisson distribution; we expect that days of cannabis use (and any substance use and days of abstinence) will not be an exception. Linear mixed effects models will be used to examine the effect of treatment group on changes in the ASI Drug and Alcohol composite scores during treatment and post-treatment follow-up assessments (as determined by the group-by-time interaction in the linear mixed effects regression models). The linear mixed effects model will include random intercepts and slopes to appropriately account for correlation among repeated measures and heterogeneity of variance over time; the model will be fit using PROC MIXED in SAS.

**McLean Hospital Application to the Institutional Review Board (IRB)  
Nabilone for Cannabis Dependence Detailed Protocol**

In secondary analyses of mood outcomes, mood episodes will be assessed during treatment and post-treatment follow-up, using the QIDS, BAI, and PANAS; changes in risk of mood episodes during treatment and post-treatment follow-up assessments will be analyzed via a logistic regression model (similar to the logistic model above) that will be fit using the GEE approach (as implemented in PROC GENMOD in SAS) to account for correlation among repeated binary outcomes on the same individual. To examine the effect of nabilone on changes in risk for mood episodes during treatment and post-treatment follow-up, the logistic regression model will include the effects of treatment condition and the baseline measure of the outcome.

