**8.4. Safety Monitoring.** Nabilone has been shown to have a favorable safety profile; it has been well-tolerated in several clinical trials and no adverse events have been reported (Ware et al. 2008, Frank et al. 2008, Skrabek et al. 2008). Drug-drug interactions are not a major concern with nabilone because it does not induce cytochrome P450 3A4 isoenzymes and lacks significant 3A4 inhibitory effect (Nahas et al. 2002). Nonetheless, we will monitor safety through the standardized methods described above in the MM visits. We will have a low threshold for obtaining additional medical workup during the study if the subject reports medical symptoms. If a participant has a clinically significant laboratory or other medical abnormality that cannot be attributed to another cause, the participant's medication will be discontinued and the participant will be followed for research visits.

**McLean Hospital Application to the Institutional Review Board (IRB)  
Nabilone for Cannabis Dependence Detailed Protocol**

As discussed above in Section 8.2.i.a, the study physician will perform a physical examination and obtain an ECG at baseline and at 14 weeks. Laboratory data (urinalysis, blood chemistries, complete blood count, electrolytes, and liver function tests) will be done at baseline and at 14 weeks as well. Given that according to its labeling, nabilone should not be taken with alcohol, sedatives, hypnotics, or other psychoactive substances because they could potentiate the central nervous system effects of nabilone, urine toxicology and blood alcohol testing will be done weekly along with the twice weekly quantitative THC urine screens during treatment. Women of childbearing potential will have urine pregnancy tests weekly each time a urine sample is given in addition to pregnancy tests at weeks at 4, 10, and 14 weeks during treatment; women who become pregnant will have their medication discontinued and will be referred to an obstetrician; like all participants, they will still be followed for research visits.

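### Section 8.9 plans no analysis of the other-substance use that 8.5.2.c announces, and its any-substance day count cannot isolate a change in alcohol or other-drug use

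*Combined protocol and SAP*

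**What the plan says.** Section 8.5.2.c (Other Drug and Alcohol Use Assessment) states that, beyond cannabis, "we will examine other substance use (using urine screens plus days of other substance use". The next sentence names the derived counts: "We will use this method to determine the number of days of cannabis use and of any substance use (and conversely, days of abstinence". The same section describes the Weekly Drug and Alcohol Use Inventory, which participants complete "indicating their number of days using marijuana, other drugs, and alcohol during the previous week". Table 8.1 schedules the Inventory at baseline, weekly, at weeks 4 and 10, and at week 14.

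Section 8.9 (Statistical Analysis) directs the secondary substance-use analyses at "the number of days of cannabis use and of any substance use (and conversely, days of abstinence) during treatment and post-treatment follow-up". These counts "will be analyzed via a log-linear (or Poisson) regression model, controlling for pre-treatment frequency of days of cannabis use". It then adds: "In addition, we will also examine the ASI Drug and Alcohol composite scores". Those scores are to be analysed by linear mixed models with a group-by-time test.

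Section 8.5.2.a has the urine samples screened for other drugs of abuse as well as for the THC metabolite, and 8.4 (Safety Monitoring) schedules weekly urine toxicology and blood alcohol testing. Section 8.9 names no analysis of these non-cannabis results. The term any substance use is not defined anywhere.

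**The concern.** An announced measure, with data collected for it, has no planned analysis. The nearest outcome in 8.9 is a union: a day counts if cannabis or anything else was used. It cannot tell a participant with unchanged habits from one who has added drinking on cannabis days, or from one who has exchanged cannabis days for drinking days.

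The comparison has some clinical weight. Section 8.4 notes that, according to its labeling, "nabilone should not be taken with alcohol, sedatives, hypnotics, or other psychoactive substances". Whether the nabilone arm drinks or uses other drugs more or less than the placebo arm is therefore something a reader of the results will want to see, and the plan as written does not produce it directly. Section 9.4 excludes current dependence on other drugs or alcohol, but not their use, so such use can occur among those enrolled.

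**Working it through.** The documents state no figure on this point, so there is nothing to reproduce. The check has three steps.

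**1. Measures announced in 8.5.2.c against analyses in 8.9**

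| Measure | In 8.5.2.c | Analysis in 8.9 |
|---|---|---|
| Days of cannabis use | yes | log-linear/Poisson, baseline cannabis days |
| Days of any substance use, days of abstinence | yes | same model, same covariate |
| Days of other substance use | yes | none |
| Urine screens for other substances | yes | none |
| ASI Drug and Alcohol composites | yes | linear mixed models |

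**2. What the any-substance count can show**

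Per 7-day week, let C be cannabis days, O days of any other substance, and A any-substance days. Then A lies between max(C, O) and min(7, C + O). If the overlap is independent, A = 7[1 − (1 − C/7)(1 − O/7)]. The values of C and O below are assumptions; the documents give none.

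- Daily cannabis unchanged, other use up: C = 7, O from 2 to 5. A = 7 before and after, while O changes by a ratio of 5/2 = 2.5.
- Daily user cuts down, other use level: C from 7 to 4, O = 2. A falls from 7 to 7[1 − (3/7)(5/7)] = 4.86 (range 4 to 6).
- Daily user cuts down, other use up: C from 7 to 4, O from 2 to 5. A falls from 7 to 7[1 − (3/7)(2/7)] = 6.14 (range 5 to 7).
- Non-daily user cuts down, other use level: C from 4 to 2, O = 2. A falls from 4.86 to 7[1 − (5/7)(5/7)] = 3.43 (range 2 to 4).
- Non-daily user cuts down, other use up: C from 4 to 2, O from 2 to 4. A is 4.86 before and 7[1 − (5/7)(3/7)] = 4.86 after (range 4 to 6 at both times).

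The first case is exact and needs no overlap assumption. In the second and third, the fall in A is smaller when other use rises, but the possible ranges (4 to 6 and 5 to 7) overlap. A and C together hint at a change in O without identifying it.

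**3. Baseline adjustment**

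The only baseline covariate named for the day counts is cannabis days. For someone who used cannabis daily before treatment, baseline A equals baseline C and nothing is lost. For the non-daily stratum of 8.2.1.c the two can differ, and pre-treatment use of other substances goes unadjusted.

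**The case against.** The case on the other side has real force, and it limits the point in several ways.

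- A reader might infer that 8.9 substitutes one outcome for another. It does not. Section 8.5.2.c itself names the any-substance count, and 8.9 carries it over. What is missing is the other measure.
- A reader might infer that a shift from cannabis to alcohol would be hidden. The plan does not support that either: "Linear mixed effects models will be used to examine the effect of treatment group on changes in the ASI Drug and Alcohol composite scores", so the Alcohol composite is compared by arm. Cannabis days have their own model, so a fall in cannabis use stays visible, and a fall there without a like fall in any-substance days points indirectly to substitution. What remains is that the ASI is a severity measure taken only at baseline and weeks 4, 10 and 14.
- It is tempting to add that the ASI Drug composite mixes cannabis with other drugs. Section 8.5.2.c lists a single drug-use area but does not say how the composite is built, so the point does not rest on it.
- Nor does the labeling statement in 8.4 show that individual participants go unmonitored. The same sentence provides weekly toxicology and blood alcohol testing, and recent substance use is discussed at the weekly medical visits (8.3.2.a). Only the between-arm summary is absent.
- Other substance use is not one of the two aims in Section 5, the trial is a Stage 1 pilot, and 8.9 says its secondary analyses will focus on the listed counts, which need not be exhaustive. This lowers the weight of the point, but a measure announced in 8.5.2.c should still have a stated analysis.
- Total abstinence is a legitimate outcome, so there is no ground for demoting the any-substance count.

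**Conclusion.** The point holds as an omission. Section 8.9 has no analysis of days of other substance use or of the non-cannabis urine results, although 8.5.2.c announces both, and the any-substance count cannot stand in for them. For a participant using cannabis daily that count is uninformative about other use: it stays at 7 days a week. For others, its information about other use depends on an overlap that the two counts do not reveal.

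Two assumptions underlie this. One is that any substance use includes cannabis, which is the plain reading given its pairing with days of abstinence. The other is that 8.9 is the full list of planned analyses. The size of any actual shift cannot be estimated from the documents, and the examples only show what is possible. The primary outcome is unaffected. This is an inexpensive improvement to the secondary analyses that is worth making.

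**What to change.** In 8.9:

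1. Add two secondary outcomes from the Weekly Drug and Alcohol Use Inventory, during treatment and at week 14: days of alcohol use, and days of other (non-cannabis) drug use. Compare each by arm with the model used for the other day counts, adjusted for its own baseline value. Table 8.1 already schedules the Inventory at baseline.
2. Report, by arm, the proportion of urine toxicology screens positive for non-cannabis drugs.
3. Keep any substance use as a prespecified outcome, state that it includes cannabis, and adjust it for its own baseline. Name the data source as well: separate weekly totals of marijuana, other-drug and alcohol days only bound the union, because they do not show which days overlap.

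The cost is some analysis-plan text and two more secondary comparisons. No new data are needed for the two counts during treatment or at week 14. The Inventory is not scheduled at weeks 11 to 13. Section 8.2.1.e lists only diary, Actiwatch and urine collection then, and 8.5.2.b describes the diary as covering cannabis and other drug use without naming alcohol. The follow-up part of the new counts should therefore be confined to week 14 unless another source is specified.

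### Section 8.9 expects the day counts to vary far more than Poisson, but names no correction to the Poisson model it assigns them

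*Combined protocol and SAP*

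**What the plan says.** Section 8.9 introduces the day counts as secondary: "Analyses of secondary substance use outcomes will focus on the number of days of cannabis use and of any substance use". The model it assigns is "Frequency of days of cannabis use (and any substance use and days of abstinence) will be analyzed via a log-linear (or Poisson) regression model", adjusted for pre-treatment days of use.

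It then warns that in many applications "count data have variability that far exceeds that predicted by the Poisson distribution", and applies the warning to these outcomes: "we expect that days of cannabis use (and any substance use and days of abstinence) will not be an exception". The next sentence moves to the Addiction Severity Index (ASI) scores. No scale parameter, quasi-likelihood, negative binomial model, robust variance or random effect is named for the day counts, in 8.9 or anywhere else.

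The devices that 8.9 does name are tied to other outcomes:

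- GEE for urine screens, "appropriately accounting for the positive correlation among repeated urine screen assessments within the same individual"
- random intercepts and slopes for the ASI scores, "to appropriately account for correlation among repeated measures and heterogeneity of variance over time"
- GEE for mood episodes, "to account for correlation among repeated binary outcomes on the same individual"

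**The concern.** A Poisson model fixes the variance equal to the mean, and its default standard errors rely on that. The plan says it expects that assumption to fail for these outcomes and leaves the consequence open. If the default output is used and the counts are overdispersed, confidence intervals are too narrow by a factor of the square root of the dispersion, and chance differences between nabilone and placebo look like drug effects too often. Leaving the correction open also allows it to be chosen after the results are known.

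A second feature complicates the direction. Days cannot exceed the length of the period, and section 8.2.1.c makes daily users one of two strata. If many participants keep using almost every day, use days have little room to vary and can be less variable than Poisson, while abstinent days are strongly overdispersed. Separate Poisson models for use and abstinence could then give conflicting tests from the same data.

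**Working it through.** The plan gives no alpha, dispersion or error rate for these outcomes, so there is no figure of its own to reproduce.

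**Inputs from the documents.** A target of 30 completers per group (8.2); 10 weeks of treatment, so at most 10 x 7 = 70 days (8.1); follow-up over weeks 11-14, so 4 x 7 = 28 days (8.2.1.e); strata of daily and non-daily users (8.2.1.c); adjustment for baseline days (8.9).

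**Assumed.** Two-sided alpha of 5%; dispersion phi (variance divided by mean); within-person correlation of daily use (ICC); share of daily users (50% or 80%); level of use during the trial.

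**Step 1: error of the uncorrected test.** If the variance is phi times the mean, the true standard error is sqrt(phi) times the Poisson one, so the actual error is 2 x P(Z > 1.96/sqrt(phi)).

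| phi | 1.96/sqrt(phi) | actual error |
|---|---|---|
| 0.5 | 2.77 | 0.6% |
| 1 | 1.96 | 5.0% |
| 2 | 1.39 | 16.6% |
| 5 | 0.88 | 38.1% |
| 10 | 0.62 | 53.5% |

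**Step 2: direction when days are capped.** For m days with mean share p used, the dispersion relative to Poisson is (1-p)(1+(m-1)ICC) for use days and p(1+(m-1)ICC) for abstinent days. Setting each to 1 with m = 70 gives the ICC above which the count is overdispersed:

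| p | use days: (1/(1-p) - 1)/69 | abstinent days: (1/p - 1)/69 |
|---|---|---|
| 0.60 | 1.5/69 = 0.022 | 0.667/69 = 0.010 |
| 0.80 | 4/69 = 0.058 | 0.25/69 = 0.004 |
| 0.95 | 19/69 = 0.275 | 0.053/69 = 0.001 |

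Away from the ceiling a small ICC is enough for overdispersion. At p = 0.6 and ICC = 0.1, for example, phi is 0.4 x 7.9 = 3.16 for use days and 0.6 x 7.9 = 4.74 for abstinent days. At p = 0.95, use days are underdispersed unless the ICC exceeds 0.275.

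**Step 3: simulated null trials.** 60 participants, stratified allocation, no true effect, log baseline days in the model, complete data, 2,000 trials per setting (simulation standard error about 0.5 percentage points at a 5% rate). Plain Poisson error:

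| Assumed pattern | 70 days, use | 70 days, abstinent | 28 days, use | 28 days, abstinent |
|---|---|---|---|---|
| All at 60% of baseline use, ICC 0.05-0.4 | 15-59% | 19-62% | 4-41% | 6-44% |
| Some quit or nearly quit | 43-71% | 52-68% | 23-55% | 35-55% |
| All at 95% of baseline (extreme, near ceiling), ICC 0.05-0.4 | 0-37% | 48-69% | 0-16% | 30-57% |

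**Step 4: the same log-linear model with a correction.** Both period lengths; the first two patterns are pooled as off the ceiling:

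| Correction | off ceiling, use | off ceiling, abstinent | near ceiling, use | near ceiling, abstinent |
|---|---|---|---|---|
| Pearson scale | 3.4-6.7% | 2.6-5.3% | 1.4-2.5% | 4.5-12.0% |
| Robust (sandwich) | 4.2-7.0% | 4.3-6.7% | 5.0-7.2% | 5.6-10.2% |

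A separate check with 30 per arm, 70-day capped counts, mean use share 0.3-0.7 and ICC 0.05-0.3 gave 8-61% for plain Poisson, 3.4-6.4% with a Pearson scale and t reference, and 5.4-7.8% with robust standard errors. With ICC 0 the counts were underdispersed and plain Poisson error fell to 0.1-1.5%.

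**The case against.** The strongest reply is that the plan has seen the problem itself, and an analyst who wrote that warning would presumably act on it. A reader might infer that the trial will report uncorrected standard errors. The documents do not say so, and the error rates above describe an analysis the plan never commits to. What stands is that the named model, followed as written, carries default standard errors that the plan itself expects to be wrong, and no replacement is fixed in advance.

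Three other strong readings also fail.

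- **That this undermines the primary analysis.** Sections 8.1 and 8.9 do list self-report data among the primary measures, but 8.9 ties the Poisson model to secondary day counts and uses GEE for the urine screens. Nor can Poisson be called the only analysis bearing on self-reported use, since 8.1 says in general terms that mixed-model ANOVA will be used. That general statement supplies no dispersion correction for the counts.
- **That the day counts alone were denied a correction every other outcome received.** The GEE and random effects are given for correlation among repeated measures. One total per person has no repeated measures, and the plan does not say whether counts will be totals or the weekly reports collected under 8.5.2.c.
- **That error is always inflated.** Step 2 shows that the cap can reverse the direction for use days.

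It is also fair that these are exploratory outcomes in a pilot and that the simulation ranges are wide because their inputs are unknown. Both points lower the priority; neither supplies the missing sentence.

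**Conclusion.** The gap is real and narrow. Section 8.9 names a Poisson model for three secondary day-count outcomes, predicts that its variance assumption will fail, and names no remedy. If default standard errors were used and the plan's expectation held, error at an assumed two-sided 5% would be about 17%, 38% and 54% at dispersion 2, 5 and 10. The documents give neither alpha nor dispersion, so the size is conditional. Close to the ceiling, intervals for use days can instead be too wide. The near-ceiling figures depend most on assumed inputs. The urine-screen GEE is not touched, and for secondary outcomes in a Stage 1 pilot this is a low-priority should-fix.

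**What to change.** Add one sentence to 8.9: the planned log-linear model for days of use and abstinence, keeping the baseline-days covariate, will be fitted with robust (sandwich) standard errors, or with a Pearson scale. Name one of the two in advance. In the simulations, robust errors held up better for use days near the ceiling, where the Pearson scale was conservative; the Pearson scale with a t reference was slightly less liberal elsewhere. The plan should note that with either choice, error for abstinent days can still reach about 10-12% if most participants keep using nearly every day.

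An optional alternative is a Pearson-scaled binomial model for days used out of days observed. It treats use and abstinence as complements, so the two cannot conflict. Simulated error was 4.2-6.6% off the ceiling and 4.6-8.0% near it with complete data. With assumed dropout it was 6.4-8.6% when dropout was random and 5.2-11.6% when dropout followed a participant's own use, so this option needs a stated approach to dropout. It also reports odds ratios instead of rate ratios.

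The cost of the minimum change is a sentence and a line or two of code; section 8.9 already plans the mood analysis "as implemented in PROC GENMOD in SAS", and that procedure can fit the corrected model. The downside is that intervals will usually be wider.
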